### **9.5.4 PK/PD**

Not applicable.

## **9.6 Interim analyses**

No interim analyses are planned for this study.

## **9.7 Sample size calculation**

The sample size of 72 patients evaluable for the primary endpoint in the study is based on pragmatic considerations and per agreement with EU Pediatric Committee (PDCO), not based on statistical considerations. It is assumed that approximately 10% of patients will not complete the trial so that 80 patients need to be randomized to ensure 72 patients will be evaluable for the primary endpoint.

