### **Treatment epoch (Visit 201-Visit 299)**

If the patient continues to meet eligibility criteria, Visit 201 (randomization/ Day 1) occurs on the same day as Visit 199. Qualifying patients will be randomized to one of the two treatment groups below, with an equal (1:1) randomization ratio:

- Indacaterol acetate 75 µg delivered via Concept1 o.d. in the morning
- Indacaterol acetate 150 µg delivered via Concept1 o.d. in the morning

The treatment epoch will last 2 weeks. Patients will receive their first dose of study medication at the site, and the patient's parent/legal guardian should be instructed to give their child study medication at approximately the same time each day. Patients will return to the clinic 2 weeks later for the end of treatment visit (Visit 299).

All patients will be required to attend the clinic visits (Visit 201 and 299) where they will take their morning fluticasone dose, have pre-dose trough measurements of lung function prior to taking the study medication, and post-dose measurements.

Parents/legal guardian(s) will be instructed to record the time of their child's last dose of study medication taken the day prior (~Day 13) to their final treatment visit (Visit 299/Day 14). Additionally, parents/legal guardians should be instructed that their child should not take the last dose of study medication on the day of the last clinic visit (Visit 299/ end of treatment). Rather, the patient (parent/legal guardian) should bring their medication with them to the clinic and this dose will be administered under the supervision of study personnel. If study medication has not been taken in the morning on day 13 (last day before end of treatment Visit 299), the visit has to be rescheduled.

PK sampling (taken  $\leq$  2 hours pre-dose and at 15 minutes and 1 hour post-dose) will be performed at Visit 199/201 and 299 ([Table 6-1](#) through [6-3](#)). The ACQ-IA will also be done at Visit 299.

[figure not shown]
Patients should be seen for all visits on the designated day or as close as possible.

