## 4 Population

The study population will consist of approximately 80 male and female children  $\geq 6$  years and  $< 12$  years with persistent asthma for at least 1 year and on stable ICS dose (with or without additional controller medication, GINA step 2 & 3) for at least 4 weeks prior to study start. It is anticipated that approximately 200 patients will need to be screened in order to randomize 80 patients into the treatment epoch.

It is intended that approximately 72 patients will complete the study. Dropouts may be replaced if dropout rate is higher than expected ( $>10\%$ ).

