#### **5.5.4 Instructions for prescribing and taking study treatment**

Patients will be provided with medication as described in [Section 5.1](#).

Study medication prescribed and dispensed to the patient and all dose changes during the study must be recorded on the Dosage Administration Record CRF (e-CRF).

At Visit 1 all patients (and parent/legal guardian) will be instructed how to use the inhalers to administer rescue salbutamol/albuterol and the fluticasone propionate correctly. Patients and parent/legal guardian will be trained to use the peak flow meter and e-Diary as well.

Beginning at Visit 101, patients will be fully trained in the correct use of the Concept1 inhaler device used to administer study medication. Patients/parents who are unable to use the device correctly will not be eligible to enter the treatment epoch. Additional training devices will be supplied for demonstration purposes. At clinic visits the investigator should check the patient's use of the inhalational device to ensure that the child is using the device correctly. Additional device training may be provided if required.

At randomization, the patient will take a single inhalation, from the Concept1 device, while at the site.

**Patients, along with their parent/ legal guardian will be instructed to take one inhalation from the Concept1 device once daily, at approximately the same time each day during the two-week timeframe. Dosing should be done in the morning, following the patient's morning dose of fluticasone propionate.** Parents/legal guardian should be instructed to rinse the child's mouth after inhalation of study drug. Water used for mouth rinsing should be

spat out and should NOT be swallowed. Patients should take their 2nd dose of fluticasone propionate in the evenings.

**The time of study medication taken on morning of Day 13 (or one day prior to Day 14/Visit 299/End of Treatment) should be recorded by the parent and brought to the clinic at Visit 299. The child should not take study medication at home on the morning of Visit 299 (end of treatment visit). Study medication will be taken at the site on this day, under staff supervision.**

All kits of study treatment assigned by the IRT will be recorded/databased in the IRT. All used and unused study medication/packaging must be returned at each study visit and/or at the time of discontinuation.

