#### **9.4.3 Handling of missing values/censoring/discontinuations**

If any of the -45 min and -15 min values contributing to the pre-dose trough FEV1 are collected within 7 days of systemic corticosteroid use, 6 hours of rescue medication, or actual measurement times are outside the 22 - 25 hour from last dose of the previous day (Day 13) then the individual FEV1 value will be set to missing.

If one of the two values is missing (or set to missing) then the remaining non-missing value will be taken as pre-dose trough FEV1. If both values are missing, or if the patient withdrew from the study, regardless of the reason for discontinuation, then pre-dose trough FEV1 will be regarded as missing in which case the missing value(s) of the patient at the particular visit(s) would not contribute to the summary statistics.

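### Section 9.7 counts completers as evaluable: 80 randomized gives about 72 expected completers but does not secure 72 evaluable children, and the Visit 299 instructions omit the trough window that can remove a completer

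*Protocol*

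**What the plan says.** **Sample size.** Section 9.7 assumes: "It is assumed that approximately 10% of patients will not complete the trial". It concludes that "80 patients need to be randomized to ensure 72 patients will be evaluable for the primary endpoint", and describes the 72 as pragmatic, agreed with the PDCO and not statistically derived. Section 4 gives the same figure as completers: "It is intended that approximately 72 patients will complete the study". It adds: "Dropouts may be replaced if dropout rate is higher than expected", meaning above 10%.

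**Evaluability.** Under Section 9.4.3 a trough FEV1 reading is set to missing if its time is "outside the 22 - 25 hour from last dose of the previous day (Day 13"), if it falls within 6 h of rescue medication, or if it falls within 7 days of systemic corticosteroids. One remaining reading is enough. With neither, the child does not contribute to the summary.

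**Visit 299 instructions.**
- Dosing is "at approximately the same time each day during the two-week timeframe" (5.5.4), and Visit 299 must be in the morning (Section 6).
- "The time of study medication taken on morning of Day 13" is to be recorded by the parent and brought to the clinic (5.5.4).
- The timing trigger for rescheduling in 3.1 is a missed dose: "If study medication has not been taken in the morning on day 13".
- Table 6-3 puts spirometry at -45 and -15 min and notes that times are approximate and may fluctuate.

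**Rescue use within 6 h.** Rescheduling is obligatory in 3.1 (Run-in epoch text, covering later visits), recommended where possible in 5.5.6, and optional in the Table 5-1 footnote.

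**Worsening asthma.** Section 5.6.2 makes worsening as defined in 6.5.6 a mandatory stop of study treatment. Section 6.5.6 lets children with night-time awakenings continue at the investigator's judgement.

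**The concern.** A completer is not necessarily evaluable under the protocol's own missing-data rule. Section 9.7 spends its whole allowance on non-completion, then describes the result as evaluable and assured. Replacement is optional and covers dropouts, not children who complete without a usable trough.

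The gap could largely be closed by scheduling, but the time limit sits only in the analysis section. Staff who follow the visit instructions can dose and measure a child in good faith and produce two readings that the analysis deletes. The same can happen if a site follows the softer rescue wording and goes ahead with the visit. The child would then have gone through the spirometry and blood draws without contributing to the primary summary.

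At stake are the agreed 72 evaluable children and a little precision in a descriptive dose comparison.

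**Working it through.** **Step 1. Reproduce the plan's figure.** Inputs from 9.7: 72 evaluable, 10% non-completion. 72 / (1 - 0.10) = 80, and 80 x 0.90 = 72.0. The figure reproduces, with nothing left over for any other loss.

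**Step 2. What 80 delivers.** With independent completion at probability 0.90 and every completer evaluable, the binomial P(X >= 72 | n = 80, p = 0.90) = 0.593. This leaves out replacement, which is optional.

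**Step 3. When timing removes a completer.** Let t be the hours from the Day 13 home dose to the clinic dose at Visit 299. The readings fall at t - 0.75 and t - 0.25 h and must lie in 22 to 25 h.
- Both usable: t - 0.75 >= 22 and t - 0.25 <= 25, so t is 22.75 to 25.25, i.e. 24 +/- 1.25 h.
- At least one usable: t - 0.25 >= 22 and t - 0.75 <= 25, so t is 22.25 to 25.75, i.e. 24 +/- 1.75 h.
- Neither usable: the clinic dose differs from the Day 13 clock time by more than 1.75 h.

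**Step 4. Possible size.** The protocol gives no spread for this shift. Assume it is normal with mean 0. Loss = P(|shift| > 1.75 h); expected evaluable = 72 x (1 - loss); standard-error factor = sqrt(1 / (1 - loss)).

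| Assumed SD | Completers lost | Expected evaluable | SE factor |
|---|---|---|---|
| 0.5 h | 0.05% | 72.0 | 1.000 |
| 0.75 h | 2.0% | 70.6 | 1.010 |
| 1.0 h | 8.0% | 66.2 | 1.043 |

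For 2% and 8% loss, the chance of at least 72 evaluable of 80 falls from 0.59 to 0.39 and 0.05.

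As a less favourable assumption, a clinic dose on average 0.5 h later than the home dose gives losses of 0.6%, 4.9% and 11.8% for the same SDs, and 71.6, 68.5 and 63.5 evaluable. The protocol does not show that such a delay occurs.

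**Step 5. Rescue use.** Readings within 6 h are deleted whichever rescheduling wording the site followed. The protocol gives no frequency, so this loss cannot be estimated.

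**Step 6. Check of the remedy.** If the home dose is within 1 h of the planned clinic-dose clock time, and the clinic dose is given as planned, t is 23 to 25. The readings then fall between 23 - 0.75 = 22.25 h and 25 - 0.25 = 24.75 h, all inside the window.

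**The case against.** The strongest reply is that little depends on this. The division is right, the surrounding text is approximate, and any plain dropout inflation yields an expected value, not a guarantee. The 72 is pragmatic and Section 9.4.2 rules out inferential testing. Controls already limit the timing loss: same-time daily dosing, morning visits, spirometry visits starting at about the same time of day (Appendix 3), a recorded Day 13 time, and the one-reading rule. The window is also in a protocol that investigators sign and sites are taken through. Sites telephone ahead about the 6 h rescue rule.

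Most of that stands, and it keeps the point small. It does not remove it. None of those controls gives an hour limit or attaches a check to the recorded time, and Table 6-3 tells sites that times may fluctuate.

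Three stronger readings are tempting and not supported:
- A reader might infer that 80 is a miscalculation or that the trial is underpowered. The arithmetic reproduces and no power was claimed.
- A reader might infer a large shortfall. The losses in the working rest on assumed spreads.
- A reader might infer that 5.6.2 and 6.5.6 also conflict over the 20% FEV1 fall and the urgent visit. Treating a child as clinically appropriate is compatible with a mandatory stop of study drug, and the general discretion over withdrawal for any listed criterion applies in Run-in. Only night-time awakening carries an express permission to continue.

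**Conclusion.** The point holds in limited form. Section 9.7 equates completers with evaluable children and should not present 72 evaluable as assured: 72 is the expected number of completers at exactly 10% non-completion, with a 0.59 chance of reaching it before optional replacement. Section 9.4.3 can reduce the number further through timing or rescue use.

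The size of that further loss is unknown and probably small. With a shift centred on zero and an SD of 0.5 to 1.0 h, it is 0.05% to 8% of completers and widens the standard error by 0 to 4.3%. A systematic delay would raise it. What is affected is slight precision and the PDCO-agreed number.

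The must/should/may difference on rescue use is a real inconsistency. The night-time awakening exception is a separate, minor inconsistency on stopping study drug and has no bearing on the sample size.

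**What to change.** 1. **Section 9.7:** drop the word *ensure* and say that about 72 completers are expected, with possibly somewhat fewer evaluable.
2. **Sections 3.1 and 5.5.4 and Table 6-3:** state the 22 to 25 h window. Ask for the Day 13 home dose within 1 h of the planned clinic-dose clock time. On arrival, check the recorded Day 13 time: wait if it is too early, and reschedule if both readings would be too late.
3. **Section 5.5.6 and Table 5-1:** use the mandatory rescheduling rule of 3.1 for rescue use within 6 h.
4. **Section 5.6.2 (separate and minor):** add the single exception that night-time awakening is left to the investigator's judgement, as 6.5.6 allows.

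The cost is wording only, with no extra patients or analyses. Some Visit 299 appointments will move, and the stated evaluable number becomes slightly less favourable.

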# **10 Ethical considerations**

## **10.1 Regulatory and ethical compliance**

This clinical study was designed and shall be implemented, executed and reported in accordance with the ICH Harmonized Tripartite Guidelines for Good Clinical Practice, with applicable local regulations (including European Directive 2001/20/EC, US CFR 21, and Japanese Ministry of Health, Labor, and Welfare), and with the ethical principles laid down in the Declaration of Helsinki.

Participation of patients in this study will be based on the local regulations and ethics committee requirements in various participating countries.

## **10.2 Informed consent procedures**

Eligible patients/subjects may only be included in the study after providing written (witnessed, where required by law or regulation), IRB/IEC-approved informed consent, or, if incapable of doing so, after such consent has been provided by a legally acceptable representative(s) of the patient. Patients below the legal age of consent are required to have the Parental Informed Consent signed by the patient's parent/guardian; children are required to sign the Assent Form (according to locally accepted policy/practice).

In cases where the patient's representative gives consent, the patient must be informed about the study to the extent possible given his/her understanding. If the patient is capable of doing so, he/she must indicate assent by personally signing and dating the written informed consent document or a separate assent form. Informed consent must be obtained before conducting any study-specific procedures (e.g. all of the procedures described in the protocol). The process of obtaining informed consent must be documented in the patient source documents.

Novartis will provide to investigators in a separate document a proposed informed consent form that complies with the ICH GCP guideline and regulatory requirements and is considered appropriate for this study. Any changes to the proposed consent form suggested by the investigator must be agreed to by Novartis before submission to the IRB/IEC, and a copy of the approved version must be provided to the Novartis monitor after IRB/IEC approval.

Girls of child bearing potential must be informed that taking the study treatment may involve unknown risks to the fetus if pregnancy were to occur during the study and agree that in order to participate in the study they must adhere to the contraception requirement for the duration of the study. If there is any question that the patient will not reliably comply, they must not be entered in the study.

### **10.3 Responsibilities of the investigator and IRB/IEC**

Before initiating a trial, the investigator/institution must obtain approval/favorable opinion from the Institutional Review Board/Independent Ethics Committee (IRB/IEC) for the trial protocol, written informed consent form, written assent form (according to local policy/practice), consent form updates, subject recruitment procedures (e.g., advertisements) and any other written information to be provided to patients/subjects. Prior to study start, the investigator is required to sign a protocol signature page confirming his/her agreement to conduct the study in accordance with these documents and all of the instructions and procedures found in this protocol and to give access to all relevant data and records to Novartis monitors, auditors, Novartis Quality Assurance representatives, designated agents of Novartis, IRBs/IECs, and regulatory authorities as required. If an inspection of the clinical site is requested by a regulatory authority, the investigator must inform Novartis immediately that this request has been made.

### **10.4 Publication of study protocol and results**

The key design elements of this protocol will be posted in a publicly accessible database such as clinicaltrials.gov. In addition, upon study completion and finalization of the study report the results of this trial will be either submitted for publication and/or posted in a publicly accessible database of clinical trial results.

### **10.5 Quality Control and Quality Assurance**

Novartis maintains a robust Quality Management (QM) system that includes all activities involved in quality assurance and quality control, including the assignment of roles and responsibilities, the reporting of results, and the documentation of actions and escalation of issues identified during the review of quality metrics, incidents, audits and inspections. Audits of investigator sites, vendors, and Novartis systems are performed by Novartis Pharma Auditing and Compliance Quality Assurance (CQA), a group independent from those involved in conducting, monitoring or performing quality control of the clinical trial. The clinical audit process uses a knowledge/risk based approach.

## **11 Protocol adherence**

This protocol defines the study objectives, the study procedures and the data to be collected on study participants. Additional assessments required to ensure safety of patients/subjects should be administered as deemed necessary on a case by case basis. Under no circumstances is an investigator allowed to collect additional data or conduct any additional procedures for any research related purpose involving any investigational drugs under the protocol.

Investigators ascertain they will apply due diligence to avoid protocol deviations. If an investigator feels a protocol deviation would improve the conduct of the study this must be considered a protocol amendment, and unless such an amendment is agreed upon by Novartis and approved by the IRB/IEC and health authorities, where required, it cannot be implemented. All significant protocol deviations will be recorded and reported in the clinical study report (CSR).

## 11.1 Protocol Amendments

Any change or addition to the protocol can only be made in a written protocol amendment that must be approved by Novartis, health authorities where required, and the IRB/IEC prior to implementation. Only amendments that are intended to eliminate an apparent immediate hazard to patients/subjects may be implemented immediately provided the health authorities are subsequently notified by protocol amendment and the reviewing IRB/IEC is notified. Notwithstanding the need for approval of formal protocol amendments, the investigator is expected to take any immediate action required for the safety of any patient included in this study, even if this action represents a deviation from the protocol. In such cases, the reporting requirements identified in [Section 7](#) Safety Monitoring must be followed.

## 13 Appendices

### Appendix 1: Instruction for Use of Concept1

#### Instructions for using inhaler and capsules.

[figure not shown]
##### **Do not swallow capsules.**

Follow the instructions below for using your inhaler. You will take the study drug contained within the capsules by inhalation using the inhaler. If you have any questions, please ask the doctor or nurse at the study center.

##### **Your inhaler and capsules**

The study drug package consists of both the inhaler and one or more blister-packaged capsules.

[figure not shown]
- Capsules are supplied in blisters.
- Inhaler consists of a cap, mouthpiece and a base.

Your inhaler is designed to deliver the medicine contained within the capsules.

Do not use the study medication capsules with any other capsule inhaler, and do not use the inhaler to take any other capsule medicine.

##### **How to use your inhaler**

**Pull off cap.**

[figure not shown]
**Open inhaler:**

Hold the base of the inhaler firmly and tilt back the mouthpiece. This opens the inhaler.

**Prepare capsule:**

Immediately before use, with dry hands, separate one of the blisters from the blister card by tearing along the perforations and lift the corner of the foil.

**Remove a capsule:**

Peel away the foil and remove the capsule from the blister.

**Insert capsule:**

[figure not shown]
Place the capsule into the capsule chamber.

**Never place a capsule directly into the mouthpiece.**

[figure not shown]
**Close the inhaler:**

You should hear a “click” as the mouthpiece closes onto the inhaler base.

[figure not shown]

**Pierce the capsule:**

- Hold the inhaler upright with the mouthpiece pointing up.
- Pierce the capsule by firmly pressing together both side buttons at the same time. **Do this only once.**
- You should hear a “click” as the capsule is being pierced.

[figure not shown]
**Release the side buttons fully.**

**Breathe out:**

Before placing the mouthpiece in your mouth, breathe out fully.

**Do not blow into the mouthpiece.**

**Inhale the medicine**

To breathe the medicine deeply into your airways:

[figure not shown]
- Hold the inhaler as shown in the picture. The side buttons should be facing left and right. Do not press the side buttons.
- Place the mouthpiece in your mouth and close your lips firmly around it.
- Breathe in rapidly but steadily and as deeply as you can.

**Note:**

As you breathe in through the inhaler, the capsule spins around in the chamber and you should hear a whirring noise. You will experience a sweet flavor as the medicine goes into your lungs.

